# 5.3 Treatment Duration

All patients treated with either KY1044 as single agent or in combination with atezolizumab will begin study treatment on Cycle 1 Day 1. Each cycle will consist of 21 days ( $\pm$ 3 days). The next scheduled dose (as single agent or in combination) may be delayed by up to 7 days to recover from previous Aes. If the next dose (as single agent or in combination) cannot be administered within the above mentioned 7-day delay, then the dose should be skipped. Dosing will resume at the scheduled dose or the next lower dose. Dose modifications should follow Section 5.6.

If more than one consecutive dose of KY1044 as single agent or in combination with atezolizumab has to be skipped due to study treatment-related toxicities, then the default position is that IMPs should be permanently discontinued. However, if a patient who misses more than one consecutive dose due to a study treatment-related toxicity experiences clinical benefit, and in the opinion of the Investigator it is in the patient's best interest to remain on study, then the patient may continue treatment after discussion with the Medical Monitor.

A patient may continue treatment with KY1044 as single agent or in combination with atezolizumab within this clinical study, as long as they are continuing to derive benefit from treatment, until the patient experiences unacceptable toxicity or confirmed disease progression per iRECIST. Patients will not be withdrawn from the study due to progressive disease per RECIST 1.1, unless clinically indicated.

Criteria for treatment cessation or patient withdrawal from the study are outlined in Section 8, and management of toxicities is outlined in Section 5.6.

Patients with SD, PR, unconfirmed CR, and unconfirmed progressive disease will continue treatment in additional cycles.

Patients who meet the following criteria will NOT continue treatment in additional cycles:

- Patients who experience unacceptable toxicity.
- Patients with confirmed progressive disease. These patients will enter the Safety follow-up period unless the Investigator considers it to be in the patient's best interest to remain on the study, and after discussion with the Medical Monitor.

• Patients with an unconfirmed progressive disease who show signs of clinical deterioration or toxicity. These patients will enter the Safety follow-up period, and will continue to be followed-up until confirmed progressive disease or initiation of a new treatment.

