# 5.6 Dose Modifications and Management of Toxicities

#### 5.6.1 Dose Modifications and Dose Delays

For patients who do not tolerate the protocol -specified dosing schedule, dose adjustments are permitted to allow the patient to continue the study treatment. The following guidelines must be followed:

- If a patient experiences an AE meeting the criteria for a DLT as outlined in Section 5.5 (including events occurring after Cycle 1), treatment should be withheld. Dose modifications for toxicities related to the study medication are summarized in Table 5-5. Following resolution of the toxicity to Grade 1 or to the patient's baseline value (as outlined in the safety management guidelines in Table 5-5), the patient may resume study treatment at the same or the next lower dose level (Table 5-2, Table 5-3) assessed to be safe (on the same dosing schedule [administration every 21 days]), if there is no evidence of disease progression as per iRECIST.
- For patients in the dose escalation part of the study receiving KY1044 in combination with atezolizumab, the KY1044 dose level will be lowered to the next lower dose level. **Dose reductions of atezolizumab are not allowed.**
- The decision to resume treatment with KY1044 as single agent or in combination with atezolizumab following the occurrence of a DLT is at the discretion of the Investigator. If the Investigator considers it to be in the patient's best interest to resume therapy before the toxicity has resolved to Grade 1, or to resume without dose reduction, this may be permitted on a case by case basis, following discussion with the Medical Monitor.
- Dose reductions for KY1044 to below 0.24 mg (less than starting dose -1) are not permitted.
- If a patient who misses more than one consecutive dose due to study treatment -related toxicity experiences clinical benefit, and in the opinion of the Investigator it is in the patient's best interest to remain on study, then the patient may continue treatment after discussion with the Medical Monitor.

- Patients who discontinue study treatment for a study related AE or a study -related abnormal laboratory value must complete their EOT visit and safety followup procedures as described in Section 5.6.2 below and be followed up for PFS and survival (please refer to Section 8.2.2).

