# 5.6.2 Follow-up for Toxicities

- The emergence of irAEs may be anticipated based on overall experience in clinical studies with similar immunomodulators.
- An irAE is a clinically important AE of unknown etiology associated with the study • drug exposure. IrAEs are typically low grade and self-limited, often occurring after multiple doses, and most frequently involving the GI tract (diarrhea/colitis), skin (rashes), liver (hepatitis), and endocrine systems (a variety of endocrinopathies) and lung (pneumonitis). Serologic, histologic (tumor sample) and immunological assessments should be performed as deemed appropriate by the Investigator, to verify the immune related nature of the AE, and exclude the neoplastic, infectious or metabolic origin of the AE. Management Algorithms (Table 5-5) have been developed to assist Investigators in assessing and managing the following groups of Aes: Infusion reactions, Hematological, Cardiological, GI, Renal, Pulmonary, Hepatic, Endocrinopathy, Dermatological, Neurological, Ophthalmological, and Rheumatological Aes.
- Patients whose treatment is interrupted or permanently discontinued due to an irAE, AE or clinically significant laboratory value, must be followed-up at least once a week (or more frequently if required by institutional practices, or if clinically indicated) for 4 weeks, and subsequently at approximately 4-week intervals, until resolution or stabilization of the event, whichever comes first. Appropriate clinical experts should be consulted as deemed necessary.
- In case of a suspected irAE, the relevant immunological assessments (eg, rheumatoid factor, anti-deoxyribonucleic acid (DNA) Ab, etc.) should be performed and guidelines as outlined in Table 5-5 (and laboratory assessments Section 6.5.6) should be followed.

All patients must be followed up for irAEs, Aes and SAEs for 90 days following the last dose of KY1044 as single agent or in combination with atezolizumab.

Table 5-5 outlines the follow-up evaluation recommended for selected toxicities. For any irAEs/Aes Grade 1 and/or Grade 2, treatment with KY1044 and atezolizumab (if applicable) should be maintained at the determined dose and schedule, unless otherwise specified in Table 5-5.

10-Nov-2021 Version number: 1

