Notes: Progressive or Grade 3 unexplained thrombocytopenia: consider work up for autoimmune disease and rule out DIC or other cause of thrombocytopenia that may be related to underlying disease Precipitous development of thrombocytopenia: consider steroid intervention pending clinical condition (brain metastases, colitis, etc.) and evaluate for immune-mediated thrombocytopenia Permanently discontinue ICI for clinically significant, steroid refractory ICI-associated thrombocytopenia				
Lymph	openia			
3	<0.5-0.2x10  /L	• Maintain dose level for study treatment-related ≤Grade 3		
4	<0.2x10  /L	• Dose delay for study treatment-related Grade 4 until resolved to ≤Grade 3		
		• Study treatment-related Grade 4 lymphopenia or leukopenia does not require discontinuation		
RENAI	_			
Grade	CTCAE description	Management	Specialist referral	
Nephrit	is (Creatinine increase)			
1	Creatinine >1.5–2xabove baseline; >0.3 mg/dL	• Continue ICI but initiate work-up to evaluate possible causes and monitor closely		
2	Creatinine >2-3xabove baseline	• Dose delay for study treatment-related ≥Grade 2 until resolved to ≤Grade 1		
		• Start corticosteroids (Note 3)		
		Discontinue ICI for persistent or recurrent elevation		
3	Creatinine >3xbaseline or	Hold ICI		
	>4 mg/dL Hospitalization indicated	• Consider resuming treatment if Grade 3 resolves (Note 2) and cause of event is confirmed. Timing of event and response to treatment should be considered in making a decision		
		

Start corticosteroids (Note 3)

Discontinue ICI for persistent or recurrent elevation

		
4	Creatinine >6.0xULN Life threatening consequences dialysis indicated	
 
Discontinue for study treatment-related Grade 4
 
Start corticosteroids (Note 3)
 
	✓	

Property of the Sanofi Group - strictly confidential

PAGE 70 OF 217

Amended Clinical Trial Protocol 07 KY1044/SAR445256-KY1044-CT01/TCD17370 - alomfilimab 10-Nov-2021 Version number: 1

Notes:

1. Grades are those listed under 'acute kidney injury' in CTCAE.

- 2. Consider using increase from baseline rather than absolute value for creatinine monitoring, especially in patients with primary renal carcinoma or other baseline renal conditions.
- 3. For persistent creatinine elevation ≥Grade 2 with no other identifiable cause, start corticosteroids. Dose and schedule should be individualized and based on grade. Taper corticosteroids when creatinine improves to Grade 1.

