НЕРАТ	TIC				
Hepatit	Hepatitis				
Grade	CTCAE description	Management	Specialist referral		
1	AST, ALT >ULN-3xULN; total bilirubin >ULN- 1.5xULN	
 
Continue ICI
 
CMP or hepatic function panel once weekly
 
If liver enzyme and function tests are stable, reduce frequency of blood tests
 
			
2	AST, ALT >3-≤5xULN; total bilirubin >1.5-≤3xULN	
 
Hold ICI
 
Rule out viral hepatitis, autoimmune disease, biliary obstruction, new metastasis or thrombosis
 
Start prednisone 0.5-1 mg/kg/day (or equivalent dose of methylprednisolone) with 4-week taper
 
Monitor CMP twice a week
 
Liver biopsy is optional
 
Resume ICI when corticosteroid taper to 10 mg/day (toxicity Grade ≤1)
 
			
3 and 4	AST, ALT >5xULN; total bilirubin >3xULN	
 
Permanently discontinue ICI
 
Monitor CMP every 1–2 days
 
Start prednisone 1–2 mg/kg/day 
 
If refractory after 3 days, consider mycophenolate
 
 
 
If liver enzymes improve, taper corticosteroid over 4 weeks
 
Consider liver biopsy
 
 a is due to the indirect (non-conjugated) component only, and hemolysis as the etiology has been ruled of the indirect (non-conjugated) component only.	out as per institutional		
guidelin	guidelines (eg, review of peripheral blood smear and haptoglobin determination), then reduce one dose level and continue treatment at the discretion of the Investigator.				

Property of the Sanofi Group - strictly confidential

PAGE 71 OF 217
Amended Clinical Trial Protocol 07 KY1044/SAR445256-KY1044-CT01/TCD17370 - alomfilimab 10-Nov-2021 Version number: 1

Asymptomatic amylase and/or lipase elevation			
3 4	>2.0-5.0xULN >5.0xULN	Any study treatment-related Grade $\geq 3$ isolated amylase or lipase abnormality that is not associated with symptoms or clinical manifestations of pancreatitis does not require dose delay or discontinuation. The Kymab Medical representative should be consulted for such amylase or lipase abnormalities.	
Note: A and/or li	CT scan or other imaging study to pase. If asymptomatic Grade 2 ele	assess the pancreas, liver, and gallbladder must be performed within 1 week of the first occurrence of any vations of lipase and/or amylase occur again at the reduced dose, patients will be discontinued permanently	$r \geq$ Grade 3 of amylase from study treatment.
CARDI	AC		
Grade	CTCAE description	Management	Specialist referral

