		
 
If no improvement in 48 h, increase corticosteroid dose to prednisone 2 mg/kg/day (or equivalent dose of methylprednisolone)
 
		
		
 
If patient improves
 
		
		
 
Taper corticosteroid over 4–6 weeks may be needed
 
		
		
 
Resume ICI when corticosteroid is tapered to ≤10 mg/ day and patient remains symptom-free (Grade ≤1)
 
		
		
 
Continue ICI monotherapy
 
		
		
 
If using combination anti-CTLA-4/ICI immunotherapy, continue ICI agent only
 
		
		
 
ICI dose reduction is not recommended
 
		
		If colitis returns on resuming ICI:		
		• Grade $\leq 2$ : temporarily hold ICI		
		• Grade $\geq$ 3: permanently discontinue ICI		
3 and 4	Grade 3: Severe abdominal pain; change in bowel habits;	• Grade 3: withhold ICI; consider resuming ICI when corticosteroid is tapered to ≤10 mg/day and patient remains symptom-free (Grade ≤1). Consider hospitalization		
	medical intervention indicated;	Grade 4: permanently discontinue ICI and hospitalize		
	diarrhea frequency $\geq 7 \times /day$ ]	Blood and stool infection work-up, inflammatory markers, imaging, endoscopy and GI consult		
	Grade 4: Life-threatening	• Start intravenous prednisone 1-2 mg/kg/day (or equivalent dose of methylprednisolone) immediately		
	intervention indicated urgent	
 
If patient improves, follow instructions for 'If patient improves' for Grade 2
 
		
		• If refractory or no improvement on IV corticosteroid, start prednisone 2 mg/kg/day (or equivalent dose of methylprednisolone) for 3 days		
		• Consider other anti-inflammatory agents eg, infliximab 5 mg/kg, which can be given again after two weeks if a second dose is needed. Vedolizumab may also be used (see Note 4).		
Notes.				
1. CBC	with differential, CMP, ESR and	CRP are recommended before starting immunotherapy, to provide baseline values for comparison over time.		
Despite the association between elevated ESR and CRP and colitis, some insurance companies may not cover these tests.				
2. There is no proven role for prophylactic corticosteroids (budesonide) to prevent GI irAEs. 				
3. Response to infliximab generally occurs within 1–3 days although some patients benefit from a second dose after 2 weeks. Prolonged oral prednisone taper may be required after infliximab administration. Whether infliximab reduces the anti-tumor efficacy of ipilimumab remains unknown. 				

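### Amylase/lipase rule in Table 5-5: recurrent asymptomatic Grade 2 forces a permanent stop, while isolated asymptomatic Grade 3 or 4 requires neither delay nor stop

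*Protocol*

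**What the plan says.** The amylase/lipase entry in Protocol Table 5-5 has rows for Grade 3 (above 2 and up to 5 times ULN) and Grade 4 (above 5 times ULN) only. For any isolated, treatment-related abnormality at those grades without symptoms or signs of pancreatitis, it states that this "does not require dose delay or discontinuation". It asks for consultation with the sponsor's medical representative, and the Note adds imaging within a week of the first Grade 3 or higher occurrence.

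The Note's second sentence turns to asymptomatic Grade 2. If such elevations "occur again at the reduced dose, patients will be discontinued permanently" from study treatment.

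The default for Grade 1 and 2 events is in Section 5.6.2: treatment "should be maintained at the determined dose and schedule, unless otherwise specified in Table 5-5". Lower KY1044 doses come from general rules. Section 5.3 says of a skipped dose: "Dosing will resume at the scheduled dose or the next lower dose". Section 5.6.1 says that after an event meeting DLT criteria has resolved, "the patient may resume study treatment at the same or the next lower dose level". Atezolizumab may not be reduced (Section 5.6.1), so a reduced dose can only be a KY1044 dose.

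**The concern.** Within one entry, the less severe laboratory finding carries the stricter action. A patient on a reduced KY1044 dose whose Grade 2 elevation returns must leave treatment for good. If the value returns at Grade 3 or 4 instead, the row requires neither a delay nor a stop. The Note also relies on a dose reduction that the entry never orders, so a site cannot tell from the entry how the patient came to be on that dose.

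The stop is costly to the patient. Inclusion criterion 4 (Section 4.2) admits people with no available therapy known to help, or who have exhausted such options. Under Section 8, a combination patient who must stop KY1044 for an adverse event must also stop atezolizumab. These stops would then appear in the SAP's summaries of TEAEs leading to discontinuation (SAP Section 10.7.1).

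**Working it through.** There is no figure in the plan to reproduce. The check compares rules, plus one count of sampling times.

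**Required action by grade in the amylase/lipase entry**

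| Asymptomatic finding | Delay required | Permanent stop required | Reduction prescribed in the entry |
|---|---|---|---|
| Grade 2, recurring at a reduced dose | superseded by the stop | yes | no |
| Grade 3, isolated | no | no | no |
| Grade 4, isolated | no | no | no |

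One grade of three carries a mandatory stop, and it is the lowest. The row does not forbid stopping at Grade 3 or 4; it does not require it.

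**Could a missing sign explain it?** Reading the Note as Grade 2 or above would extend the stop to Grades 3 and 4, where the row says none is required. The contradiction would move, not disappear.

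**Where can the reduced dose come from?** Not from this entry. Where Table 5-5 intends a reduction it says so: the hepatitis note on indirect bilirubin reads "then reduce one dose level and continue treatment at the discretion of the Investigator". For amylase or lipase the patient must already have been reduced through Section 5.3 or 5.6.1. The Note can therefore be triggered, but only by way of rules outside the entry.

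**Do other recurrence rules in Table 5-5 behave this way?**

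- Colitis ("If colitis returns on resuming ICI"): Grade 2 or lower is a temporary hold; Grade 3 or higher is a permanent stop.
- Creatinine: "Discontinue ICI for persistent or recurrent elevation" appears at both Grade 2 and Grade 3, and Grade 4 is a stop outright.

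Neither becomes milder as grade rises. The amylase/lipase entry alone ties its recurrence stop to Grade 2 and leaves Grades 3 and 4 without one.

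**What applies if the Note's second sentence is removed?** Section 5.6.2 defers to Table 5-5 only where the table says something different. Without the sentence, asymptomatic Grade 2 returns to the default of unchanged dose and schedule.

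**How often is the finding looked for?** Amylase and lipase belong to the clinical chemistry panel (Table 6-8).

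- Cycle 1, Days 1, 8 and 15: 3
- Cycle 2, Days 1, 8 and 15: 3
- Cycle 3, Days 1 and 8: 2
- Total 3 + 3 + 2 = 8. The Cycle 1 Day 1 sample is pre-dose, so 8 − 1 = 7 fall after the first dose by Cycle 3 Day 8, then one per cycle.

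This measures the opportunity to detect an elevation. It is not a trigger rate.

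**The case against.** The best defence is that the two rules address different situations. The row gives the general position for Grade 3 and above, while the Note covers recurrence after a reduction has already been tried. A lower stopping threshold at that point could be a deliberate step-down rule, and a specific recurrence rule may qualify a general one. But the row covers *any* such abnormality, so recurrences at Grade 3 or 4 fall under it too. A patient on a reduced dose is still treated more strictly at Grade 2 than at Grade 4.

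A second argument is that Grade 3 and 4 elevations do have dose consequences elsewhere. Table 5-4 lists no amylase or lipase exception to its Grade 3 and 4 DLTs, and Section 5.6.1 withholds treatment for an event meeting DLT criteria. Whether an asymptomatic value is clinically relevant enough to meet the DLT definition is arguable. Even if it is, that route gives a hold and possibly a lower dose, with no mandatory permanent stop. It offers a plausible origin for the reduced dose and shows a tension between the row and Sections 5.5 and 5.6.1. That is a separate matter and does not restore the order of severity.

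Three points stand. The reach is narrow. The sponsor's intent cannot be read from the documents. If the Note errs, it errs towards stopping drug, so deleting the sentence does give up an automatic stop in a first-in-human study.

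**Conclusion.** The concern holds. As written, the entry requires permanent discontinuation for recurrent asymptomatic Grade 2 elevation at a reduced dose and requires neither delay nor discontinuation for the same isolated abnormality at Grade 3 or 4. This rests on the current text alone and needs no numerical assumption.

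The practical size is small but unknown. It affects only patients already on a reduced KY1044 dose with a treatment-related, asymptomatic Grade 2 elevation that recurs. Section 6.5.6 also requires a single asymptomatic laboratory abnormality to be repeated before it counts as an adverse event. The documents give no rate for this combination. Sample size and error rates are unaffected. It should be corrected because an affected patient loses treatment permanently, including atezolizumab in the combination arm, for the lesser finding.

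**What to change.** Delete the second sentence of the Note, the one on asymptomatic Grade 2 elevations recurring at the reduced dose. Grade 2 then follows Section 5.6.2. Keep imaging and sponsor consultation for Grade 3 and above. Section 8 still lets the Investigator or Medical Monitor stop treatment for an adverse event judged to contraindicate further dosing, which limits the loss of the automatic Grade 2 stop.

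If the sponsor does want a recurrence stop, three changes are needed together:

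- attach the stop to Grade 3 and above, in the direction of the colitis rule;
- write the KY1044 reduction step into the row;
- limit the row's exemption from delay and discontinuation to the first occurrence.

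The cost is one sentence deleted, or restated with a reduction step and a limit on the row, at the next protocol amendment. Sample size, assessments and analyses do not change.

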#### Amended Clinical Trial Protocol 07 KY1044/SAR445256-KY1044-CT01/TCD17370 - alomfilimab

10-Nov-2021 Version number: 1

		• If central hypothyroidism, replace thyroid hormone (see above) after corticosteroids have been initiated	
Note: In	the uncommon scenario of MRI fi	ndings without pituitary deficiency, consider high dose corticosteroids for prevention of hormonal dysfunc	tion.
* Hypop	ohysitis is not defined in CTCAE V	ersion 4.0. This classification is drawn from the CTCAE category 'Endocrine disorders - Other'.	
Hypoth	yroidism		
Grade	CTCAE description	Management	Specialist referral?
1	Asymptomatic; clinical or	
 
Hold ICI for ≥Grade 3 irAEs
 
	1
	diagnostic observations only; intervention not indicated	• ICI can be continued after resolution of symptoms to Grade 2 or better.	
2	Symptomatic; thyroid replacement indicated; limiting instrumental ADL	• Start standard thyroid replacement therapy: initial dose can be the full dose (1.6 mcg/kg) in young, healthy patients, but a reduced dose of 25-50 mcg should be initiated in elderly patients with known cardiovascular disease.	
3	Severe symptoms; limiting self-care ADL; hospitalization	• Repeat TSH and free T4 testing after 6-8 weeks and adjust thyroid hormone dose accordingly. If TSH is above reference range, increase thyroid hormone dose by 12.5 mcg to 25 mcg	
4	Life-threatening consequences;	• After identification of the appropriate maintenance dose, further evaluation is required every year, or sooner if patient's status changes	
	urgent intervention indicated	• After identification of the appropriate maintenance dose, further evaluation is required every year, or sooner if patient's status changes	
Hypert	ıyroidism		
Grade	CTCAE description	Management	Specialist referral?
1	Asymptomatic; clinical or	• Hold ICI for ≥Grade 3 irAEs	1
	diagnostic observations only; intervention not indicated	Standard therapy for hyperthyroidism should be followed	
2	Symptomatic; thyroid	• Thyroiditis is self-limiting and has 2 phases:	
	suppression therapy indicated; limiting instrumental ADL	
 
In the hyperthyroid phase, patients may benefit from beta blockers if symptomatic (eg, atenolol 25-50 mg daily, titrate for HR <90 bpm if BP allows). Monitor closely with regular symptom
 
	
3	Severe symptoms; limiting self-care ADL; hospitalization indicated	evaluation and free T4 testing every 2 weeks.	

Property of the Sanofi Group - strictly confidential

PAGE 74 OF 217

